6.2.4. Dose Administration

Investigational product will be provided as an oral suspension. **Ganaxolone must be taken with a meal or snack.** Note: grapefruit and grapefruit juice, Seville oranges and star fruit are prohibited during the study.

Ganaxolone oral suspension will be administered through an oral dosing syringe administered by parents/caregivers TID, following the morning, noon, and evening meal or snack. Each dose should be separated by a minimum of 4 hours and a maximum of 12 hours. A missed dose of investigational product may be taken up to 4 hours before the next scheduled dose; otherwise, the missed dose should not be given.

Prior to each dose, the following instructions should be followed:

1. Manually shake bottle end to end, 2-3 times per second, for 1 minute
2. Allow the bottle to stand for 1 minute
3. Attach the dosing apparatus (adaptor with syringe), invert the bottle and remove the indicated dose
4. Administer dose as indicated

Use the bottle adapter and dosing syringes provided. Do not use a household spoon. The syringe should be replaced daily and cleaned between each dose that day by rinsing for 30 seconds using hot water and allowing it to air dry. The bottle adapter should stay in the bottle once it's inserted. It should not be removed.

Subjects and their parent or legal guardian will be informed about possible side effects from the investigational product and cautioned to avoid quick postural changes, at least until they know how the investigational product affects them. Subjects will be advised that the investigational product might affect mental alertness. They will also be cautioned that non-adherence to the dosing instructions (e.g., increasing the dose, taking the investigational product doses too close together) could produce side effects.

6.2.5. Missing a Dose

Ganaxolone oral suspension: A missed dose of investigational product may be taken up to 4 hours before the next scheduled dose; otherwise, the missed dose should not be given.

Parents/caregivers should be instructed that if the subject misses 2 days in a row or more, the site should be contacted to determine whether any adjustment in investigational product is needed. The site will confer with the medical monitor to devise a dosing plan.

Parents/caregivers should be instructed to minimize the number of missed doses the subject experiences and be re-educated on proper dosing procedures at each visit to ensure that missed doses are avoided.

Table 13: Missed Dose of Investigational Product

Formulation	Proceed to Dose	DO NOT DOSE
Suspension	≥ 4 hours before next scheduled dose	< 4 hours before next scheduled dose

6.4. Labeling, Packaging, Storage, and Handling

6.4.1. Labeling

Labels containing study information and bottle identification are applied to the investigational product container.

All investigational product is labeled with a minimum of the following: protocol number, medication identification number (if applicable), dosage form (including product name and quantity in pack), directions for use, storage conditions, batch number and/or packaging reference, the statements “For investigational use only” and/or “Caution: New Drug—Limited by Federal (or US) Law to Investigational Use” and “Keep out of reach of children,” and the sponsor’s name and address.

Additional labels may, on a case-by-case basis, be applied to the investigational product in order to satisfy local or hospital requirements, but must not:

- Contradict the clinical study label
- Obscure the clinical study label
- Identify the study subject by name, without consultation with the sponsor

Additional labels may not be added without the sponsor’s prior full agreement.

6.4.2. Packaging

Ganaxolone and PBO oral suspension formulation will be provided to the site as individual suspension bottles containing 110 mL in 125-mL HDPE bottles. Ganaxolone will be supplied at a concentration of 50 mg/mL.

Changes to sponsor-supplied packaging prior to dosing may not occur without full agreement in advance by the sponsor.

6.4.3. Storage

The investigator has overall responsibility for ensuring that investigational product is stored in a secure, limited-access location. Limited responsibility may be delegated to the pharmacy or member of the study team, but this delegation must be documented. Investigational products are distributed by the pharmacy or by a nominated member of the study team.

Ganaxolone and PBO suspension should be stored at room temperature 15°C to 25°C (59°F to 77°F).

Investigational product must be stored in accordance with labeled storage conditions. Temperature monitoring of the investigational product is required at the storage location to ensure that the investigational product is maintained within an established temperature range. The investigator is responsible for ensuring that the temperature is monitored throughout the duration of the study and that records are maintained; the temperature should be monitored continuously by an in-house system, by a mechanical recording device such as a calibrated chart recorder, or by manual means, such that both minimum and maximum thermometric values over

a specific time period can be recorded and retrieved as required. Such a device (i.e., certified min/max thermometer) would require manual resetting upon each recording. The sponsor must be notified immediately upon discovery of any excursion from the established range. Temperature excursions will require site investigation as to cause and remediation. The sponsor will determine the ultimate impact of excursions on the investigational product and will provide supportive documentation as necessary. Under no circumstances should the product be dispensed to subjects until the impact has been determined and the product is deemed appropriate for use by the sponsor.

The sponsor should be notified immediately if there are any changes to the storage area of the investigational product that could affect the integrity of the product(s), such as fumigation of a storage room.

6.5. Investigational Product Accountability

Investigators will be provided with sufficient amounts of the investigational product to carry out this protocol for the agreed number of subjects. The investigator or designee will acknowledge receipt of the investigational product, documenting shipment content and condition. Accurate records of all investigational product dispensed, used, returned, and/or destroyed must be maintained as detailed further in this section.

The investigator has overall responsibility for administering/dispensing investigational product. Where permissible, tasks may be delegated to a qualified designee (e.g., a pharmacist) who is adequately trained in the protocol and who works under the direct supervision of the investigator. This delegation must be documented in the applicable study delegation of authority form.

The investigator or their designee (as documented by the investigator in the applicable study delegation of authority form) will administer and/or dispense the investigational product only to subjects included in this study following the procedures set out in the study protocol. Each subject will be given only the investigational product carrying his or her treatment assignment. All administered and/or dispensed investigational product will be documented on the eCRFs and/or other investigational product record. The investigator is responsible for ensuring the retrieval of all investigational product and study supplies from subjects.

The subject's parent/caregiver must be instructed to save and bring their unused investigational product and empty/used investigational product packaging to the clinic and final follow-up visit or to ship it back to the site via secure courier. Investigational product accountability must be assessed at the container/packaging level for unused investigational product that is contained within the original tamper-evident sealed container (e.g., bottles) or at the individual count level for opened containers/packaging. The pharmacist/nominated person will record details on the investigational product accountability form.

No investigational product stock or returned inventory from a Marinus-sponsored study may be removed from the site where originally shipped without prior knowledge and consent by the sponsor. If such transfer is authorized by the sponsor, all applicable local, state, and national laws must be adhered to for the transfer.

The sponsor or its representatives must be permitted access to review the supplies storage and distribution procedures and records.

At the end of the study, or as instructed by the sponsor, all unused stock, subject-returned, or expired investigational product are either to be sent to a nominated contractor on behalf of the sponsor for destruction or are to be destroyed by the site. Investigational products being returned to the sponsor's designated contractors or approved to be destroyed by the site counted/measured and verified will be reconciled by clinical site personnel and the sponsor (or designated CRO). Shipment return forms, when used, will be signed prior to shipment from the site. Returned investigational products will be packed in a tamper-evident manner to ensure product integrity. Shipment of all returned investigational product must comply with local, state, and national laws.

With the written agreement of the sponsor, unused stock, subject-returned, and expired investigational product may be destroyed at the site or a local facility. In this case, destruction records identifying what was destroyed, when, and how must be obtained with copies provided to the sponsor. Destruction of investigational products must be in accordance with local, state, and national laws.

Based on entries in the site's drug accountability forms, it must be possible to reconcile investigational products delivered with those used and returned. All investigational products must be accounted for and all discrepancies investigated and documented to the sponsor's satisfaction.

6.6. Subject Compliance

Subject compliance will be tracked through the electronic seizure and medication diary. Parent/caregiver are to record daily seizure frequency and type in addition to study medication and non-study AED administration throughout the study including the prospective 6-wk baseline seizure-charting period. Compliance with investigational product treatment will be assessed by inspecting the electronic seizure and medication diary entries and returned supplies with queries as necessary. Parent/caregiver will be re-educated on the importance of adhering to daily seizure, investigational product and non-study AED recording as needed. Subjects that fall below 80% compliance at 2 consecutive visits during the double-blind phase will not be included in the per-protocol population.

7. STUDY PROCEDURES

7.1. Study Assessments

See Schedule of Assessments ([Table 1](#) and [Table 2](#)) for details regarding scheduled assessments and procedures in this study.

7.2. Study Procedures (Double-blind Phase)

7.2.1. Screening Period

7.2.1.1. Historical Seizure Type and Frequency (Week -14)

Potential subjects will have already been pre-identified by the site because of confirmed or suspected CDKL5 genetic mutation testing as part of their standard of care epilepsy work-up.

It is also very common that parents/caregivers/LARs of CDKL5 patients maintain daily seizure calendars, which capture both seizure type and frequency and days when no seizures occur as part of their standard of care treatment regimen. A 2-month (8-week) daily historical seizure calendar will be reviewed at the screening visit to determine eligibility per inclusion/exclusion criteria. Acceptable daily historical seizure calendars will need to denote seizure types, frequency, and days that no seizures occurred. Procedures specific to this protocol and not otherwise considered standard of care, will not be performed until written informed consent/assent from the subject's parent or legal guardian has been appropriately obtained. In the event that parents/caregivers/LAR do not routinely maintain a daily seizure calendar per standard of care, written informed consent will be obtained, and the subject will be asked to return to the clinic for the Screening (Visit 1) after they have maintained a 2-month (8-week) daily historical seizure calendar.

7.2.1.2. Screening (Visit 1, Week -6)

Additional procedures/assessments to be completed during the screening period may include the following:

- Informed consent from parent/LAR (or subject assent)
- Demographics and medical history
- Historical seizure calendar review
- Review of inclusion/exclusion criteria
- Genetic testing to confirm pathogenic or likely pathogenic CDKL5 variant
- Seizure Identification and Diagnostic Review Form (SIF/DRF) (Epilepsy Study Consortium)
- Vital signs (to include BP, HR, RR, body temperature, weight, and height)
- Physical, neurological, and developmental examination
- ECG

- Clinical laboratory tests (to include complete blood count [CBC] with automated differential, creatinine, blood urea nitrogen, and comprehensive metabolic panel)
- Urinalysis (An attempt should be made to collect a urine sample at this screening visit. Otherwise, the urine sample can be collected at baseline.)
- Drug screen (urine or plasma)
- Investigator and parent/caregiver/LAR establish baseline patient behavior for CGICA, CGI-C and CGI-I
- Serum pregnancy test for girls/women of childbearing potential
- Tanner staging
- Concomitant AED review and levels if per standard of care (SOC)
- Neurosteroid level sample draw
- Adverse events
- Electronic seizure and medication diary set up and review

A screen failure is a subject for whom informed consent has been obtained and has failed to meet the inclusion criteria and/or met at least 1 of the exclusion criteria and has not been administered the investigational product.

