Caregiver Global Impression of Change in Seizure Intensity/Duration (CGI-CSID)						X	X		X
Clinical Global Impression Improvement (CGI-I) by parent/caregiver & clinician		X ^m				X	X		X
			█						█
			█			█	█		█
			█			█	█		█
			█			█	█		█
			█			█	█		█
Dispense Investigational Product			X			X	X		X

Table 1: Schedule of Assessment for the 17-week, Double-blind Treatment Phase of the Study

	Screen/Baseline			DB Titration + Maintenance					Final DB Visit
WEEK	-14	-6 (Screening)	0 Baseline (Randomization)	3 days	1, 2, 3, 4	5	9	11, 13	17
Visit Windows			+6 days ⁿ	± 1 day	± 3 days	± 3 days	± 3 days	± 3 days	± 3 days
	Historical Seizure frequency	Visit 1	Visit 2	Phone Follow-up	Phone Follow-up	Visit 3	Visit 4	Phone Follow-up	Visit 5

AED = antiepileptic drug; BP = blood pressure; CBD = cannabidiol; D/C = discontinuation; DB = double-blind; ECG = electrocardiogram; EEG = electroencephalogram; HR = heart rate; LAR = legally authorized representative; PK = pharmacokinetic; RR = respiratory rate; THC = tetrahydrocannabinol; WCBP = women of childbearing potential.

- a. Written informed consent/assent must be obtained from subject, parent or LAR before any study assessments are performed.
- b. Written informed consent/assent from subject, parent or LAR needed if 8-week historical control is not available and need to chart prospectively.
- c. Review of medical history only.
- d. Genetic testing to be performed to confirm pathogenic or likely pathogenic CDKL5 variant.
- e. In addition, height and weight will be measured. If weight unable to be collected at Visit 1, may be collected at Visit 2.
- f. In addition, weight will be measured.
- g. Chemistry & Hematology ([Section 12.2](#)).
- h. An attempt should be made to collect a urine sample for a urinalysis at screening. Otherwise, the urine sample can be collected at baseline for the urinalysis.
- i. A drug screen (urine or plasma) will be performed to test for THC and CBD at screening. A negative drug test at screening meets the protocol eligibility criteria. If the screening drug test is positive, a plasma drug screen will be performed to test for THC and CBD at baseline. A positive drug test at baseline will exclude the subject from the study.
- j. Serum pregnancy test is required for all girls/women of childbearing potential.
- k. Population PK will be conducted at these visits (Visit 3: between 1-5 hours since last IP dosing, Visit 4: between 4-8 hours since the last IP dosing).

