- l. Concomitant AEDs or their dose must be stable for 1 month prior to screening and cannot be changed at any time prior to Visit 5 but may be adjusted during the open-label phase of the study.
- m. During the Screening visit, the investigator and parent/caregiver/LAR will decide on a specific behavior that the patient exhibits that denotes assessment measured. This behavior will be used at subsequent visits to assess change after the initiation of investigational product.
- n. Visit 2 to occur minimum of 6 weeks (42 days) after Visit 1 and maximum of 6 weeks + 6 days (48 days)

Table 2: Schedule of Assessments for Open-Label Phase

	Final DB Visit/ First OL Visit	Titration (4 weeks blinded)					Open-Label Maintenance (Visits will be every 16 weeks with a telephone follow up in-between after 52 weeks)						Final OL Visit or Taper	Safety Follow-up post
WEEK	17	3 Days Post Visit 5	18	19	20	21	28	34	43	52	60	68 and X visit	X/ or early D/C	2 weeks post last
Visit Windows		± 1	± 3 days	± 3 days	± 3 days	± 3 days	± 7 days	± 7 days	± 7 days	± 7 days	± 7 days	± 7 days	± 7 days	± 3 days
	Visit 5	Phone follow-up	Phone follow-up	Visit 6	Phone follow-up	Visit 7	Phone follow-up	Visit 8	Phone follow-up	Visit 9	Phone follow-up	Visit 10 and Visit X	Visit X	Visit X
Safety Assessments														
Vital signs (BP, HR, RR, and body temperature) ^a	X ^a			X		X		X ^{a b}		X ^{a b}		X ^a	X ^{a b}	X
Physical/Neurological/Developmental Exam	X					X		X		X		X	X	
Physical/Neurological/Developmental Exam Follow-up				X										X
ECG	X					X		X		X		X	X	
Clinical Laboratory Tests ^c	X			X	X	X		X		X		X	X	X
Urinalysis	X									X ^e			X	X ^e
Pregnancy Test (WCBP) ^d													X	X
Tanner Staging ^e										X			X	
Investigational Product PK	X			X		X ^f		X		X ^f		X	X	X
Concomitant AED Review and levels if per standard of care	X			X		X		X		X		X	X	X

Table 2: Schedule of Assessments for Open-Label Phase

	Final DB Visit/ First OL Visit	Titration (4 weeks blinded)					Open-Label Maintenance (Visits will be every 16 weeks with a telephone follow up in-between after 52 weeks)						Final OL Visit or Taper	Safety Follow-up post
WEEK	17	3 Days Post Visit 5	18	19	20	21	28	34	43	52	60	68 and X visit	X/ or early D/C	2 weeks post last
Visit Windows		± 1	± 3 days	± 3 days	± 3 days	± 3 days	± 7 days	± 7 days	± 7 days	± 7 days	± 7 days	± 7 days	± 7 days	± 3 days

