9.7.2. Key Secondary Efficacy Endpoints

The key Secondary endpoints are:

- Number (%) of subjects with a $\geq 50\%$ reduction from baseline in primary seizure frequency.
- Clinical Global Impression of Improvement (CGI-I) at the last scheduled visit in the 17-week DB treatment phase.

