12.7. Appendix 7: Clinical Global Impression - Improvement (CGI-I)

For the Clinician:

Date: _____

Subject No: _____

Rater Initials: _____

Subject Initials: _____

Rate the overall global impression of change after the start of investigational product relative to baseline (prior to investigational product). Please circle the appropriate number.

1. **Very much improved**
2. **Much improved**
3. **Minimally improved**
4. **No change**
5. **Minimally worse**
6. **Much worse**
7. **Very much worse**

Clinical Global Impression - Improvement (CGI-I) for the Caregiver

Date: _____

Subject No: _____

Rater Initials: _____

Subject Initials: _____

Rate the overall global impression of change after the start of investigational product relative to baseline (prior to investigational product). Please circle the appropriate number.

- 1. Very much improved**
- 2. Much improved**
- 3. Minimally improved**
- 4. No change**
- 5. Minimally worse**
- 6. Much worse**
- 7. Very much worse**

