### 1.2.2 Secondary Efficacy Endpoints

Derived seizure secondary efficacy endpoints will be based on data through the end of the 17-week DB treatment phase relative to the 6-week prospective baseline phase.

Seizure control:

- Change from baseline in the percentage of seizure-free days during the 17-week DB treatment phase, based on the primary seizure types
- Number (%) of subjects with a  $\geq 50\%$  reduction from baseline in primary seizure frequency
- Caregiver Global Impression of Change in Seizure Intensity/Duration (CGI-CSID).

Behavioural/Neuropsychiatric:

- Caregiver Global Impression of Change in Attention (CGICA) score
- Clinical Global Impression-Change (CGI-C) in parent/caregiver/LAR identified behavioural target - potential domains include sociability, communication, irritability, and hyperactivity
- Clinical Global Impression of Improvement (CGI-I): overall improvement by both parent/caregiver/LAR and clinician.

- [REDACTED]
- [REDACTED]
- [REDACTED]
- [REDACTED]

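### Table 1 in both documents ties CGI-I to one behaviour fixed at screening, while the SAP definition and the rating forms ask for overall change

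*Protocol*

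**What the plan says.** Two descriptions of CGI-I stand in the current text.

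**Overall change.** SAP Section 1.2.2 lists "Clinical Global Impression of Improvement (CGI-I): overall improvement by both parent/caregiver/LAR and clinician". Protocol Appendix 7 has one form for the clinician and one for the caregiver, and both print the same instruction: "Rate the overall global impression of change after the start of investigational product relative to baseline (prior to investigational product").

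**A behaviour chosen at screening.** Protocol Table 1 has a row headed "Clinical Global Impression Improvement (CGI-I) by parent/caregiver & clinician", and its screening cell carries superscript m. Footnote m reads "During the Screening visit, the investigator and parent/caregiver/LAR will decide on a specific behavior that the patient exhibits that denotes assessment measured", and continues "This behavior will be used at subsequent visits to assess change after the initiation of investigational product". Table 1 of the SAP has the same row, superscript and footnote. Protocol Section 7.2.1.2 also names CGI-I alongside the two behaviour-anchored scales: "Investigator and parent/caregiver/LAR establish baseline patient behavior for CGICA, CGI-C and CGI-I".

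**Status and analysis.** Protocol Section 9.7.2 names two key secondary endpoints, and one is "Clinical Global Impression of Improvement (CGI-I) at the last scheduled visit in the 17-week DB treatment phase". The SAP has no key-secondary tier and places CGI-I with the behavioural and neuropsychiatric secondary endpoints. Protocol Section 9.7 and SAP Section 7.1.7 confine formal testing to the primary endpoint. SAP Section 7.1.3.4 summarises CGI-I by the count and percentage at each point of the seven-point scale.

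**The concern.** Footnote m describes how CGICA and CGI-C work: agree a concrete behaviour before treatment, then rate change in that behaviour. Attached to CGI-I, it gives raters an instruction that conflicts with the question printed on the form. A child whose seizures improve clearly, but whose chosen behaviour does not, could be rated as improved under the form and as unchanged under the footnote. If raters differed in which instruction they followed, the reported CGI-I distribution would mix two constructs. The completed forms would not show which was used, because they have no place to record it.

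**Working it through.** No figure in the plan depends on this point, so the check is a comparison of texts.

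**Step 1: which scales the footnote belongs to.**

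| Scale | Footnote m at screening (Table 1, both documents) | Named behaviour in the scale's own description | Line for a behaviour on the form |
|---|---|---|---|
| CGICA | Yes | Yes (Protocol 7.4.3) | Yes (Appendix 4) |
| CGI-C | Yes | Yes (Protocol 7.4.4) | Yes (Appendix 5) |
| CGI-CSID | No screening entry | No (Protocol 7.4.2) | No (Appendix 6) |
| CGI-I | Yes | No in SAP 1.2.2; text of Protocol 7.4.5 not available | No (Appendix 7, both forms) |

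For CGICA and CGI-C, the schedule, description and form agree. CGI-CSID, which is also a rating of change from baseline, has no screening step. CGI-I is the only scale of the four whose schedule entry calls for a behaviour that its form cannot record.

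**Step 2: what each text instructs.** The sentence saying the chosen behaviour is used at later visits to assess change appears in footnote m. Section 7.2.1.2 says only that baseline behaviour is established. It shows that putting CGI-I with the other two scales was not confined to a superscript, but it gives no scoring rule.

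**Step 3: whether precedence resolves it.** SAP Section 11 lets the SAP override the protocol. The SAP holds the overall definition in Section 1.2.2 and footnote m on the CGI-I row of its own Table 1, so the rule has nothing to choose between.

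**Step 4: the missing section.** Protocol Section 7.4.5, on CGI-I, is in the table of contents, but its text is not in the copy available for review. It may well state the overall construct. Whatever it says, footnote m remains on CGI-I in both schedules.

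**Step 5: direction and size of any effect.** Suppose a fraction f of raters, equal in the two arms because treatment is blinded, scores one behaviour. For the percentage of subjects above any chosen cut of the scale, the expected observed difference is

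observed = (1 − f) × overall difference + f × behaviour difference.

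The documents give none of these three quantities. Purely as assumptions, take an overall difference of 25 percentage points and a behaviour difference of 5:

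- f = 0.25: 0.75 × 25 + 0.25 × 5 = 20 points
- f = 0.50: 0.50 × 25 + 0.50 × 5 = 15 points
- f = 1: 5 points

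If the behaviour difference were also 25 points, the result would be 25 at every f. Dilution therefore occurs only if the effect on the single behaviour is the smaller one, and its size is set entirely by the assumptions.

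**The case against.** The strongest reply is that the intended construct is not in doubt. Raters complete the Appendix 7 form, and both versions ask for overall change. The protocol's visit lists attach the caregiver-identified target to CGI-C and only the names of the raters to CGI-I. Section 7.4 mentions CGI-I separately from behavioural change. Footnote m looks like one generic note shared by three rows, and its reference to whatever is being assessed could be stretched to mean overall condition. Any scale rated against baseline also needs a documented pre-treatment picture.

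Much of this stands. It makes widespread mis-scoring unlikely to be the default, and it confirms which text should be kept. It does not remove the conflict. The footnote speaks of a specific behaviour and says that this behaviour is what later visits use. Section 7.1 sends sites to Tables 1 and 2 for details of assessments, so the schedule is a working instruction.

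A reader might infer more than the documents support:

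- *That Section 7.2.1.2 itself tells raters to score CGI-I on one behaviour.* It does not; it concerns only the baseline.
- *That CGI-I will in practice be scored on one behaviour.* The printed forms point the other way. Mixed scoring is possible but not shown to be likely.
- *That CGI-I would duplicate CGI-C.* Footnote m does not say the two scales share a behaviour.
- *That the trial loses power or that type I error changes.* The plan performs no test on CGI-I, so there is no planned power to lose.

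**Conclusion.** The inconsistency is real and present in both documents: the schedule attaches a single-behaviour rule to an endpoint that the SAP definition and the rating forms treat as overall change. Followed literally, the schedule would have CGI-I scored on the wrong construct. The consequence is limited to interpretation of CGI-I, with possible dilution of the observed GNX–placebo difference if some raters follow the footnote and if the effect on the chosen behaviour is smaller than the overall effect. The size of any dilution cannot be derived from the documents. The primary endpoint and its test are untouched. The point matters more under the protocol, which ranks CGI-I as key secondary, than under the SAP, which does not. It deserves correction because of that rank and because the correction costs very little. The conclusion rests on the wording of Table 1, SAP Section 1.2.2 and Appendix 7, not on any assumed response rate.

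**What to change.** 1. Remove superscript m from the CGI-I row of Table 1 in the protocol and in the SAP, leaving it on CGICA and CGI-C.
2. Limit the bullet in protocol Section 7.2.1.2 to CGICA and CGI-C, or state there that for CGI-I the subject's overall pre-treatment condition is what is documented.
3. Send raters a short clarification that CGI-I is rated on overall condition relative to the pre-treatment baseline, as printed in Appendix 7, and that the behaviour chosen at screening applies to CGICA and CGI-C only.

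The cost is a wording change in two tables and one bullet, plus a site memo. No procedure, visit or analysis is added.
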